### **10.2 Dissemination of Data**

The results of this project will demonstrate that daily protein intake from minimally and further processed food sources will serve as a pragmatic and efficient means for improving body protein status. Results of this study may be used for presentations, posters, or publications. The publications will not contain any identifiable information that could be linked to a subject.

### **10.3 Data Handling and Recordkeeping**

The Principal Investigator will carefully monitor study procedures to protect the safety of research subjects, the quality of the data and the integrity of the study. Paper source documents and Case Report Forms (CRFs) will be stored in a secure area of the PI's laboratory. Access will be limited to study personnel. Documents will be archived according to UAMS policies regarding destruction of research records. Data (without identifiers) will be entered into an electronic spreadsheet or database (e.g. REDCap) to facilitate analyses. These files are maintained on secure password-protected UAMS

servers. Approximately 7 years after study completion, paper and electronic records will be destroyed per UAMS disposal guidelines. At no time shall Protected Health Information be released to non-study personnel.

#### **10.4 Data Access**

All subjects will be assigned a unique identifying code or number. The key to the code (the instrument associating the data with subject identity) will be kept on a password-protected UAMS server. Only study staff members will have access to the code and information that identifies the subject in this study. This file will be deleted approximately seven years after data analysis is completed.

#### **10.5 Power Calculations**

We propose a group size of 10 per group, based upon an ANOVA model to compare the nutrition interventions. With this sample size, the ANOVA model has 80% power to detect effect sizes of  $f = 0.484$  or larger. This estimate assumes that the basal covariate explains 50% of the variation in the response and a 5%  $\alpha$ -level is used to determine statistical significance.

---

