## Study Schema

Recruiting will be performed via word of mouth, TRI subject database (ARresearch.org), and the UAMS social media platforms.

Visit 1: informed consent process takes place at the RIOA. Enrolled subjects undergo body composition test and DXA scan (or at Visit 2) using PI's equipment.  
Randomization (1:1:1) occurs.

Visit 2: subjects undergo body composition test and DXA scan if not done at Visit 1.  
Run-in meals are dispensed.

Visit 3: Subjects report fasted to the RIOA to begin a 13-hour visit that entails stable isotope ingestion, blood/urine/saliva sampling and study meal ingestion.

Visit 4: Subjects report fasted to the RIOA the morning after visit 3 to undergo blood, saliva, urine and muscle sampling approximately 24 hours after isotope ingestion.

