**1.0 Protocol Summary**

This will be a randomized study to demonstrate how animal-based protein-rich food sources can be used by older adults to increase protein intake within pre-existing dietary patterns. In this regard, we propose to augment the current dietary pattern of older Americans by readily available quality protein sources. To this end, we will investigate the effects of recommended and common protein intakes on the maintenance of whole-body protein balance and potential for muscle protein anabolism. Plans to accomplish project goal(s): We will study 3 groups of 10 older subjects during daily protein intakes of 0.8 (recommended dietary allowance [RDA]), 1.1 (National Health and Nutrition Examination Survey [NHANES]), and 1.5 (optimal [OPI]) g/kg/d. Due to common eating patterns in older adults (1), these protein intakes will be structured within 2 meals per day. A 2-day dietary lead-in (matching the subject's intervention paradigm) will proceed each dietary intervention. Whole-body protein balance will be determined during metabolic study days by oral ingestion of 2 grams of the stable isotope N-alanine, and a 24-hr integrated value of muscle protein synthesis will be determined by ingestion of deuterated water. Oral ingestion of 10mg of 3-Methyl-d3-L-histidine and analysis of urine samples will permit measurement of muscle protein breakdown during this period. Integrated post-meal blood EAA will also be determined, as we have demonstrated a relationship between peripheral EAA response and protein anabolism.

Study duration per subject will be about 2 weeks.

---

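### Section 10.5's f = 0.484 does not follow from its own inputs: 10 per group gives f = 0.425 with the assumed covariate and f = 0.600 under the one-way ANOVA of 10.1

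*Combined protocol and SAP*

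**What the plan says.** Section 10.5 (Power Calculations) opens with "We propose a group size of 10 per group, based upon an ANOVA model to compare the nutrition interventions". It then says "With this sample size, the ANOVA model has 80% power to detect effect sizes of" f = 0.484 or larger, and adds that "the basal covariate explains 50% of the variation in the response", with a 5% significance level. Three groups of 10 are confirmed in section 1.0 ("We will study 3 groups of 10 older subjects during daily protein intakes of 0.8" g/kg/d and two higher intakes), and the Study Schema gives equal allocation ("Randomization (1:1:1) occurs"). Section 4.0 allows up to 50 enrolled and sets 30 as the target for completion.

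Section 10.1 (Statistical Analysis) plans a one-way ANOVA for every listed outcome, with post-hoc comparisons if there is a group effect. It names no covariate. Sections 8.4 and 9.4 describe a single muscle biopsy, taken at Visit 4, as the basis for muscle protein synthesis.

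**The concern.** Section 10.5 is the only sample-size justification in the protocol, and f = 0.484 is its only quantitative result. All the inputs needed to check it are stated: number of groups, group size, power, alpha and the variance explained by the covariate. The result should therefore reproduce, and it does not.

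A reader cannot tell whether the group size, the R-squared or the effect size is the misstated item. Repairing only the mismatch between 10.5 and 10.1 would not help. Adding a covariate to 10.1 leaves 0.484 wrong in one direction, and dropping the covariate from 10.5 leaves it wrong in the other.

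**Working it through.** **Inputs.** From 10.5: 10 per group, 80% power, f = 0.484, R-squared = 0.50, alpha = 0.05. From 1.0 and the Study Schema: three equal groups, so N = 30. From 4.0: 30 is the completion target, so 10 per group is already net of dropout.

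**Formula.** Power of the omnibus F test for three groups is P(F' > Fcrit), where F' is noncentral F with:
- df1 = 3 − 1 = 2
- df2 = N − 3 − c, where c is the number of covariates
- noncentrality λ = N f² / (1 − R²)

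**Step 1: the plan's figure on its own inputs.** N = 30, c = 1, R² = 0.50, so df2 = 26. At f = 0.484, λ = 30 × 0.2343 / 0.50 = 14.06 and power is 89.6%, not 80%. Solving for 80% power gives λ = 10.84, so f = √(10.84 × 0.50 / 30) = 0.425. The stated value is 0.484 / 0.425 = 1.14 times this.

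**Step 2: the model in 10.1.** N = 30, no covariate, so df2 = 27. At f = 0.484, λ = 30 × 0.2343 = 7.03 and power is 60.5%. Solving for 80% power gives λ = 10.79, so f = √(10.79 / 30) = 0.600.

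**Step 3: which inputs return 0.484 at 80% power.**

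| Per group | N | R² | f at 80% power | Power at f = 0.484 |
|---|---|---|---|---|
| 10 | 30 | 0.50 | 0.425 | 89.6% |
| 9 | 27 | 0.50 | 0.452 | 85.5% |
| 8 | 24 | 0.50 | 0.484 (0.4838) | 80.0% |
| 10 | 30 | 0 (no covariate) | 0.600 | 60.5% |

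At 10 per group with one covariate degree of freedom and R² = 0, f at 80% power is 0.601. The R² that brings this down to 0.484 is 1 − (0.484 / 0.601)² = 0.35.

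**Step 4: other readings at N = 30.**
- No degree of freedom charged for the covariate: 0.424.
- Separate covariate slopes per group (df2 = 24): 0.427.
- The 50% read as a correlation of 0.5, so R² = 0.25: 0.521.
- Chi-square approximation: 0.401.
- 90% power instead of the stated 80%: 0.487, or 0.486 with no degree of freedom charged.

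None gives 0.484. The 90% reading comes closest, but it contradicts the stated power and still misses in the third decimal.

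**The case against.** The strongest reply is that the slip is harmless. With the covariate granted, 10 per group has about 90% power at f = 0.484, so the sentence read as at least 80% power is true and understates the design. That stands: on its own terms the error is conservative. It does not rescue the figure, because 10.5 presents 0.484 as the 80%-power threshold for this sample size. The protection also disappears if no covariate is used, which is what 10.1 specifies.

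A second reply is that the mismatch between 10.5 and 10.1 is the larger problem, and that rewriting 10.5 to resolve it would remove this error too. That is fair as to priority, and the fix should start there. It also means that 0.425 should not simply replace 0.484. It would be a more optimistic figure resting on a covariate that the planned analysis does not use. For muscle protein synthesis, the single Visit 4 biopsy cannot supply a basal value.

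Three stronger readings are tempting, and the documents do not support them:
- **The figure came from a 24-subject calculation.** The match at 8 per group is close, but no section mentions 8 per group or 24 evaluable subjects, and R-squared of about 0.35 at 10 per group fits as well. The origin is unknown. A dropout allowance from 10 to 8 is not an explanation either, since 4.0 counts 30 as completers.
- **The trial is underpowered because of this error.** Under the stated covariate assumption it is not. The lower power under 10.1 comes from the missing covariate, not from the arithmetic.
- **The recruitment target or an allowance for lost biopsies was derived from 0.484.** Section 4.0 gives its numbers without reference to 10.5, and no section states a tolerance for biopsy loss.

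**Conclusion.** The concern holds as an arithmetic error in 10.5. At 10 per group the detectable effect at 80% power is f = 0.425 if one covariate with R-squared 0.50 is in the model, and f = 0.600 under the one-way ANOVA as written. The stated 0.484 lies between the two and is correct for neither: actual power there is 89.6% with the covariate and 60.5% without.

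These results assume an omnibus F test, equal groups, 30 completers, alpha 0.05 and one degree of freedom for the covariate. Not charging that degree of freedom moves 0.425 only to 0.424. The documents give no expected effect size for any outcome, so whether f = 0.600 is an acceptable detectable effect cannot be judged from them.

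**What to change.** Settle the model first, then recompute 10.5 for it:

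1. If 10.1 stays a one-way ANOVA without a covariate, state that 10 per group gives 80% power for f = 0.600, and remove the covariate assumption.
2. If a covariate is wanted for some outcomes, name it in 10.1, say when it is measured, and quote f = 0.425 (R-squared 0.50) for those outcomes only. Keep f = 0.600 for any outcome without a basal measurement, which includes muscle protein synthesis as currently sampled.
3. If 0.484 is the intended target, state the group size and R-squared that produce it. At R-squared 0.50 it corresponds to 8 evaluable subjects per group; at 10 per group it corresponds to R-squared of about 0.35.

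The cost is a sentence or two in 10.5, plus one in 10.1 if a covariate is added. The correction itself requires no change to enrolment or procedures.

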Visit 3: This visit will take place at the UAMS RIOA on the morning after subject completes the 2-day run-in meals. At this visit, subjects will report having fasted for 10 or more hours. This visit is expected to take about 13 hours. During this visit, subjects will be asked to provide blood/urine/saliva samples. They will ingest deuterated water (~3mL per kg body weight) at specific times (total dose divided into 10 aliquots and ingested every hour up to study hour 9:00) and 2g of a stable isotope of alanine (15N-alanine) dissolved in water. Two (group-specific) study meals will be served, one in the morning and one in the afternoon/evening. See **Figure 2** for a timeline. After the second saliva sample has been collected, subjects will go home and return to the study site the following morning having fasted overnight.

Visit 4: This visit will take place at the UAMS RIOA on the morning after visit 3. Subjects will fast overnight between visits 3 and 4. Approximately 24-hours after isotope ingestion, the final biological samples will be collected and the subject offered a snack and beverage. They will then be dismissed.

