## **8.4 Muscle**

At Visit 4, qualified and credentialed study staff (M.D. or PA) will perform a vastus lateralis muscle biopsy of the subject's outer thigh using 1% plain lidocaine for anesthesia. Approximately 100mg of muscle tissue will be obtained using a Bergstrom needle. The tissue will be rinsed with normal saline and flash frozen using liquid nitrogen. The sample will be transferred into a labelled cryo tube and frozen at < -60 degrees C in the PI's lab.

---

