### **9.4 Muscle**

MPS will be determined by oral D2O ingestion to assess 24-hr muscle protein synthesis using the single biopsy approach (26). In the interest of brevity, the sample preparation methods are standard in the PI's laboratory and have recently been outlined in detail (27). Muscle preparations will be analyzed for incorporation of deuterated alanine by GC-MS using partial integration (28). The daily rate of muscle protein synthesis will be determined according to Gasier et al. (27).

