### **10.1 Statistical Analysis**

Means by which experimental data will be analyzed or interpreted: Changes in whole-body protein synthesis, breakdown, flux, net balance, muscle protein synthesis, and plasma EAA area under the curve (AUC) between groups will be assessed with a one-way analysis of variance (ANOVA). In the event of a main effect of group, appropriate post-hoc comparisons will be carried out. Statistical significance will be accepted at an alpha level of  $p \leq 0.05$ .

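### The 80% power in Section 10.5 depends on a basal covariate that the planned one-way ANOVA does not contain; for muscle protein synthesis and whole-body kinetics, power at f = 0.484 is about 60%

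*Combined protocol and SAP*

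**What the plan says.** Section 10.5 (Power Calculations) sets the sample size: "We propose a group size of 10 per group, based upon an ANOVA model". It claims 80% power for effect sizes of f = 0.484 or larger at a 5% alpha level, and attaches a condition: "This estimate assumes that the basal covariate explains 50% of the variation in the response". The covariate is not identified there or anywhere else.

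Section 10.1 (Statistical Analysis) is the only description of the analysis. It opens with "Changes in whole-body protein synthesis, breakdown, flux, net balance, muscle protein synthesis" and plasma EAA AUC, and says that these "between groups will be assessed with a one-way analysis of variance (ANOVA"). No covariate is named. Pairwise testing is conditional: "In the event of a main effect of group, appropriate post-hoc comparisons will be carried out".

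On measurement times, Section 5.0 places Visit 3 "on the morning after subject completes the 2-day run-in meals", and Section 1.0 says that the lead-in diet matches the subject's assigned intervention. Section 8.4 gives the only muscle sample: "At Visit 4, qualified and credentialed study staff (M.D. or PA) will perform a vastus lateralis muscle biopsy". Section 9.4 confirms a single-biopsy method. Section 9.2 derives whole-body synthesis, breakdown, flux and net balance from one 24-hour urine collection after labelled alanine, taken across Visits 3 and 4.

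**The concern.** The power figure belongs to a model with a covariate, and the planned model has none. A covariate that explains half the variance roughly doubles the effective sample size, so this is not a small discrepancy.

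For muscle protein synthesis and whole-body kinetics, the design also gives no basal value that could fill the role. Both are measured once, after the subject has started the assigned diet. For these outcomes, *Changes* in 10.1 can only mean differences between groups.

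Section 10.5 is the only justification of the sample size, and Section 3.0 frames the hypothesis in terms of muscle protein synthesis and whole-body protein balance. A reader would take a null result to come from a test with 80% sensitivity at f = 0.484. Because post-hoc comparisons follow only a significant overall test, too low a chance of passing that test also blocks the comparisons behind the stepwise RDA, NHANES, OPI ordering.

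**Working it through.** **Inputs.** Three groups, equal allocation (7.0). Ten per group, f = 0.484, covariate R² = 0.50, alpha 0.05 (10.5). One-way ANOVA (10.1). Thirty completers (4.0), so N = 30 is the number analysed. Equal variances are assumed.

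**Method.** Power = P(F′ > critical F), where F′ is noncentral F with 2 and df₂ degrees of freedom and noncentrality λ.
- One-way ANOVA: λ = N f², df₂ = N − 3.
- ANCOVA with one covariate, f on the raw SD: λ = N f²/(1 − R²), df₂ = N − 4.
- ANCOVA with f already on the covariate-adjusted SD: λ = N f², df₂ = N − 4.

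**Step 1: try to reproduce the stated 80%.** Section 10.5 does not say which SD scales f, so both readings were tried.

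| Model | n per group | λ at f = 0.484 | df₂ | Power at 0.484 | f for 80% power |
|---|---|---|---|---|---|
| ANCOVA, raw SD | 10 | 30 × 0.484²/0.5 = 14.06 | 26 | 89.6% | 0.425 |
| ANCOVA, adjusted SD | 10 | 30 × 0.484² = 7.03 | 26 | 60.3% | 0.601 |
| ANCOVA, raw SD | 8 | 24 × 0.484²/0.5 = 11.24 | 20 | 80.0% | 0.4838 |

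Neither reading gives 80% at 10 per group. The stated pair does come out at 8 per group on the raw SD. That suggests, but does not prove, that the calculation was made for another group size. It also makes the raw SD the likelier scale for f.

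These ANCOVA figures treat the covariate as balanced between groups. Simulating a random covariate with R² = 0.5 gives about 88.4% at 10 per group, so the conclusion does not change.

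**Step 2: the analysis actually planned.** One-way ANOVA, 10 per group, λ = 30 × 0.484² = 7.03, df 2 and 27:
- power at f = 0.484 is 60.5% (60.6% by simulation);
- 80% power needs f = 0.600;
- the chance of missing f = 0.484 is 100 − 60.5 = 39.5%.

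If f = 0.484 was meant on the adjusted SD, the raw f is 0.484 × √0.5 = 0.342 and power is 33.5%.

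**Step 3: the same in SD units.** With equal steps between groups, the RDA-to-OPI difference is 2f/√(2/3). That is 1.19 SD at f = 0.484 and 1.47 SD at f = 0.600.

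**Step 4: is there a basal value?** Before the run-in meals the documents describe height and weight, medical history, a blood count, DXA and bioimpedance (5.0, 9.5, 9.6). Isotope, urine, saliva and muscle sampling all fall in Visits 3 and 4, after the run-in. The 3-methylhistidine dose is taken the evening before Visit 3, also during the run-in. No pre-diet muscle protein synthesis or whole-body kinetic value is described. Plasma EAA is left out of the claim because its sampling times are in Figure 2, which is not shown.

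**Step 5: sample size for the stated claim.** One-way ANOVA at raw f = 0.484 gives 77.6% power with 14 per group and 80.7% with 15.

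**The case against.** The arithmetic and the mismatch between 10.1 and 10.5 are hard to dispute. The best counter-arguments are these.

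- **A basal covariate need not be the outcome's own baseline.** Weight, DXA lean mass or sex could serve. This stands in part: such variables exist before the diet. But 10.1 names none, and nothing in the documents supports R² = 0.50 for any of them.
- ***Changes* may mean change scores.** Where a basal value explains 50% of the variance, with equal variances, f becomes 0.484/√(2(1 − 0.707)) = 0.632 and power is 84%, above the claim. This is why the point is limited to outcomes without a basal value; for those there is nothing to subtract.
- **The scale of f is not stated.** True, so the 60% is conditional on the raw SD. The other reading gives a lower figure (about 34%), so the headline uses the more favourable one.
- **f = 0.484 is a detectable effect, not a target.** This stands. The 39.5% miss rate applies to a true effect of that size, and the documents do not say that this effect is expected or is the smallest that matters. It is a reason not to ask for a larger trial, but it does not make the stated power correct.
- **Nothing in the conduct of the trial changes.** Also true, but the power statement is still wrong for the outcomes in the hypothesis.

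**Conclusion.** The point holds. For muscle protein synthesis and whole-body protein kinetics, the planned one-way ANOVA with 10 completers per group has 60.5% power at f = 0.484, not 80%. It reaches 80% at f = 0.600, or 1.47 SD between RDA and OPI with equal steps. At f = 0.484 the overall test would fail, and the post-hoc comparisons would not be made, in about 4 of 10 such trials. The stated 80% is also not what 10 per group gives with the covariate included, on either reading of f.

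This rests on equal variances, 30 completers and f scaled by the unadjusted SD. It does not extend to plasma EAA. Type I error and the estimated group differences are unaffected.

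**What to change.** **Section 10.5.** Replace the second and third sentences with: *For muscle protein synthesis and whole-body protein kinetics, with 10 completers per group, a one-way ANOVA at alpha 0.05 has 80% power for f = 0.60 (SD not adjusted for covariates); power at f = 0.484 on that scale is about 60%.* Add a separate sentence for plasma EAA AUC once its analysis variable and any basal sample are stated, so that it is not left without a power figure.

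**Section 10.1.** For muscle protein synthesis and whole-body kinetics, write *Differences* in place of *Changes*.

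**If an adjusted analysis is preferred,** name in 10.1 the covariates measured before the diet (for example sex and DXA lean mass). Take the detectable f from a simulation that allows for chance imbalance. The documents give no R² for such covariates, so a range is needed. With two random covariates sharing R² equally, equal-step means, 10 per group and raw f = 0.484, simulated power is:

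| R² | 0.1 | 0.2 | 0.3 | 0.4 |
|---|---|---|---|---|
| Power | 61% | 67% | 73% | 80% |

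**Cost.** Text changes in two sections and a less favourable stated figure. No extra subjects, visits or samples are needed. A larger trial is not proposed: 80% power at f = 0.484 without a covariate would take 15 per group, or 45 completers. Under the cap of 50 enrolled, that leaves 1 − 45/50 = 10% for loss, against 1 − 30/50 = 40% now.

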#### **11.0 Risks and Benefits**

---

There will be no direct benefits to the study participants; however, knowledge gained from the study could potentially benefit patients in the future. Anticipated risks associated with this protocol are described in detail below. All experimental procedures will be performed by appropriately trained and credentialed personnel. The PI and study physician will be responsible for oversight of study procedures and evaluation of adverse events. There are no known risks of body composition testing (InBody770, BioSpace, Seoul, South Korea), urine or saliva collection.

### **11.1 Stable Isotope Ingestion**

The risks of drinking 70% deuterated water are temporary dizziness, nausea and possibly vomiting. Each dose is approximately 20-40 mL (1 ½ - 2 tablespoons). There are no known risks of ingestion of the stable isotopes of alanine or methyl histidine.

